4.8.3. Adverse Events

All treatment-emergent AEs (TEAEs) will be listed and summarized by treatment group, system organ class, preferred term, severity, relationship, and seriousness. Serious adverse events (SAEs) will be summarized by treatment group, severity, and relationship to study treatment and will be listed by patient separately.

Each patient will be counted only once within a system organ class or a preferred term using the event with the greatest relationship and greatest severity.

Specific AE will be summarized by treatment group, system organ class, and preferred term. Adverse events included will be those listed in the query from Section 3.3.2.

All information pertaining to AEs noted during the trial will be listed by patient, detailing the verbatim description given by the Investigator, preferred term, system organ class, start date, stop date, severity, action taken regarding study drug, corrective treatment, outcome, and drug

relatedness. The event onset will also be shown relative (in number of days) to the date of first study treatment administration. In addition, a list of patients who prematurely discontinue from the trial due to adverse events will also be provided.

4.8.4. Laboratory Tests

4.8.4.1. Clinical Safety Laboratory Parameters

Laboratory test results will be summarized with descriptive statistics for each treatment group at Screening, Week 4, and the Final Evaluation Visit. Changes from Screening to Week 4 and to Final Evaluation Visit also will be summarized for continuous test results. For urinalysis, the number and percentage of patients within each treatment group with a normal; abnormal, clinicially significant; and abnormal, not clinically significant result will be presented.

Shift tables (low, normal, high) will be presented to summarize laboratory test results at Screening and the Final Evaluation Visit. Normal ranges established by the central laboratory will be used to determine shifts. A listing of all out-of-range or clinically significant laboratory test results at any evaluation will be provided. Determination of clinical significance for all out-of-range laboratory values were to be made by each investigator and will be included in the listing.

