4.2.1 SCREENING VISIT

The Screening Visit must take place within 14 days prior to investigational product administration at Day 0 (Treatment Visit). The following procedures must be performed and recorded at this visit:

1. Review trial procedures and information regarding the trial and obtain written informed consent
2. Review eligibility criteria
3. Obtain medical/surgical history, including prior toxin use, and demographic information, including Fitzpatrick skin type
4. Conduct patient education: Discuss the potential effect of DaxibotulinumtoxinA for Injection treatment, explain the PFWs measurement and the categories of the severity assessment scales, and instruct the subjects to consider depth of lines for severity of their glabellar lines. Use the provided Patient Education Brochure
5. Measure and record vital signs (body temperature, respiratory rate, sitting radial pulse, and sitting systolic and diastolic blood pressure)

- [REDACTED]
7. Obtain 12-lead ECG

8. Collect blood samples for clinical safety laboratory tests (hematology, chemistry, and PT)

[REDACTED]

The screening visit clinical laboratory test results, UPT and ECG report must be reviewed and signed by the Investigator; any abnormal results must be determined to be not clinically significant by the Investigator prior to randomization.

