4.2.5 FINAL EVALUATION VISIT OR EARLY DISCONTINUATION

The following procedures must be performed and recorded at the Final Evaluation Visit for each subject. Following treatment, subjects will be followed for safety until at least Week 24 and up to Week 36 with monthly visits until both IGA-FWS and PFWS scores have returned to baseline. The subject will then have a Final Evaluation Visit.

1. Conduct patient education: Discuss the potential effect of DaxibotulinumtoxinA for Injection treatment, explain the PFWS measurement and the categories of the severity assessment scales, and instruct the subjects to consider depth of lines for severity of their glabellar lines. Use the provided Patient Education Brochure
2. Measure and record vital signs (body temperature, respiratory rate, sitting radial pulse, and sitting systolic and diastolic blood pressure)

- [Redacted]
- [Redacted]
- [Redacted]
- [Redacted]
- [Redacted]
- [Redacted]
- [Redacted]
- [Redacted]
- [Redacted]
- [Redacted]

10. Provide [Redacted] and Facial Age Self Evaluation (FASE) (section 4.6.2.4) questionnaires to subject for completion

- [Redacted]
- [Redacted]
- [Redacted]
- [Redacted]
- [Redacted]
- [Redacted]
- [Redacted]
- [Redacted]
- [Redacted]
- [Redacted]

16. Assess AEs

- [Redacted]
- [Redacted]
- [Redacted]
- [Redacted]
- [Redacted]

[REDACTED]
If there are no safety concerns, the subject's participation in the trial is complete at this visit.

After the Final Evaluation Visit, all qualified subjects will have the option to enroll into an open-label, trial to evaluate the long-term safety of repeat use of DaxibotulinumtoxinA for Injection for the treatment of moderate to severe glabellar lines.

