4.5 SAFETY ASSESSMENTS

4.5.1 CLINICAL LABORATORY DATA

As outlined in Table 3, non-fasting samples for hematology, chemistry, PT and urinalysis will be collected at Screening, Week 4, and at the Final Evaluation Visit. [REDACTED]

[REDACTED] Blood and urine will be collected using applicable safety precautions and will be processed according to the central clinical laboratory’s instructions. Urinalysis will be evaluated at the trial center using supplies provided by the sponsor.

Table 3: Clinical Laboratory Tests

Serum Chemistry	Hematology	Urinalysis	Additional Tests
Glucose	Hemoglobin	Specific gravity	Prothrombin time (PT) (Screening, Week 4 and Final Evaluation only) Urine Pregnancy (WOCBP only)* [REDACTED] [REDACTED] [REDACTED] [REDACTED]
Total bilirubin	Hematocrit	pH	
Alanine aminotransferase	Leukocyte Count (total)	Glucose	
Aspartate aminotransferase	Leukocyte Count (differential)	Protein	
Alkaline phosphatase	Red Blood Cell Count	Blood	
Blood urea nitrogen	Platelet Count	Bilirubin	
		Ketones	

*If positive at timepoints after study treatment, confirm by serum pregnancy test

It is the Investigator’s responsibility to review the results of all laboratory tests as they become available. For each laboratory test result outside the reference range, the Investigator must ascertain if the abnormal lab result is a clinically significant result for that individual subject. Likewise, if laboratory tests are taken at follow-up visits, the

Investigator must ascertain if this is an abnormal and clinically significant change pretreatment for that individual subject. The Investigator may repeat the laboratory test or request additional tests to verify the results of the original laboratory test. The Investigator must sign and date all written laboratory results (e.g., urinalysis, hematology, chemistry, PT, and pregnancy tests) and note Not Clinically Significant (NCS) or Clinically Significant (CS) for each out of range laboratory value. If a laboratory value is determined to be a clinically significant result for that subject, this may be considered an AE. Refer to Section 6.1.1 for further information.

[REDACTED]

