7.6.2 LABORATORY TESTS

Laboratory test results will be summarized with descriptive statistics for each treatment group at Screening and Final Evaluation Visit. Change from Screening to Final Evaluation Visit also will be summarized for continuous test results.

Shift tables will be presented to summarize laboratory test results at Screening and Final Evaluation Visit. Normal ranges established by the central laboratory will be used to

determine shifts. A listing of all out-of-range laboratory test results at any evaluation will also be provided. Determination of clinical significance for all out-of-range laboratory values will be made by each investigator and included in the listing. In addition, a listing of all clinically significant laboratory test results will be provided.

[REDACTED]

UPTs will be summarized for all treated subjects in the category of WOCBP by treatment group and presented in the data listings.

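### Laboratory shift tables leave out Week 4, so no table counts by arm the hematology, chemistry and PT values that cross reference limits at that visit

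*SAP*

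**What the plan says.** Protocol 4.5.1 sets the sampling schedule: "non-fasting samples for hematology, chemistry, PT and urinalysis will be collected at Screening, Week 4, and at the Final Evaluation Visit". SAP 3.3.3 has the same three visits.

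SAP 4.8.4.1 then plans these outputs:

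- Descriptive statistics: "Laboratory test results will be summarized with descriptive statistics for each treatment group at Screening, Week 4, and the Final Evaluation Visit".
- Change from Screening: "Changes from Screening to Week 4 and to Final Evaluation Visit also will be summarized for continuous test results".
- Shift tables: "Shift tables (low, normal, high) will be presented to summarize laboratory test results at Screening and the Final Evaluation Visit".
- A listing: "A listing of all out-of-range or clinically significant laboratory test results at any evaluation will be provided".
- For urinalysis, counts and percentages by treatment group in three classes: normal, abnormal and clinically significant, abnormal but not clinically significant.

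Protocol 7.6.2 restricts its shift tables in the same way and also omits Week 4 from its other summaries: "Laboratory test results will be summarized with descriptive statistics for each treatment group at Screening and Final Evaluation Visit". The SAP therefore added Week 4 to the descriptive and change summaries but left the shift tables as they were. The available text gives no reason for the difference.

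On the timing of the last sample, Protocol 4.2.5 says that "subjects will be followed for safety until at least Week 24 and up to Week 36 with monthly visits", ending once both severity scores are back at baseline. Protocol 4.2.6 asks subjects who leave early to return for the same assessments, which can fall before Week 24.

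**The concern.** A shift table shows how many subjects in each arm moved from one reference category at Screening to another after treatment. Here the only post-treatment column is a visit that, apart from early discontinuation, occurs when both severity scores have returned to baseline or follow-up has reached Week 36. A subject who is normal at Screening, out of range at Week 4 and normal again at Final Evaluation is entered as normal to normal.

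The other Week 4 outputs do not fill this gap. Means and mean changes can hide a few subjects who cross a limit. A listing shows those subjects one by one but gives no count by arm and no denominator, which matters under 2:1 allocation. At stake is whether a reader of the safety report can see, by arm, a transient laboratory shift at the one post-treatment sample taken at the same time in everyone.

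**Working it through.** The plan states no figure to reproduce, and no power or sample-size calculation bears on the point. The check is of timing and of which visits each output uses.

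**Timing.** Inputs: visit weeks from Protocol 3.1.4; a window of 3 days either side for Week 4 and Weeks 24 to 36 from Protocol 4.3, Table 2; days counted from treatment as Day 0.

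- Week 4: 4 × 7 = 28, so day 28 − 3 = 25 to day 28 + 3 = 31.
- Final Evaluation without early discontinuation: earliest 24 × 7 − 3 = 165; latest 36 × 7 + 3 = 255.
- Gap between the two samples: from 165 − 31 = 134 days to 255 − 25 = 230 days. No laboratory sample is scheduled in between.
- Screening is within 14 days before treatment (Protocol 4.2.1). Week 4 is thus not the only sample near treatment, but it is the only planned post-treatment one.

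**Coverage of hematology, chemistry and PT in SAP 4.8.4.1.**

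| Output | Week 4 | Final Evaluation | By-arm count of category changes |
|---|---|---|---|
| Descriptive statistics | yes | yes | no |
| Change from Screening | yes | yes | no |
| Shift tables (low, normal, high) | no | yes | yes, at Final Evaluation only |
| Listing of abnormal results | yes | yes | no |

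The shift tables use 1 of 2 planned post-treatment visits. With about 300 subjects there are at most 300 × 2 = 600 planned post-treatment panels, of which 300 do not enter them. That describes one output, not data lost to analysis.

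**Consistency within the SAP.** Safety endpoints in SAP 3.3.1 treat the first four weeks as a period of separate interest. SAP 4.8.2 counts injection-site reactions by arm, by visit and at any post-treatment visit. SAP 4.8.6 counts the overall ECG assessment, taken at Screening and Week 4, in categories by arm. Hematology, chemistry and PT have no equivalent Week 4 count.

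The documents give no expected rate of laboratory shifts, so the number that would go uncounted cannot be derived.

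**The case against.** The strongest reply is that Week 4 is already well covered. SAP 4.8.4.1 gives by-arm descriptive and change summaries there. Where the SAP spells out such statistics elsewhere (4.3, 4.8.1, 4.8.6) they include the minimum and maximum, so extreme values would probably show. Every abnormal result is listed with the investigator's judgment of clinical significance. Protocol 6.1 counts a clinically significant laboratory abnormality among possible adverse events, and Protocol 7.6.1 tabulates treatment-emergent events by arm up to Week 4. Urinalysis has its own categorical summary.

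Most of this stands, and it limits the point. A reader might infer that Week 4 is missing from the laboratory analysis, or that the shift tables are the only categorical laboratory comparison between arms; the documents contradict both. But the adverse-event route is not certain: Protocol 4.5.1 and 6.1.1 say only that a clinically significant value may be considered an event, and out-of-range values judged not clinically significant do not take that route. Extremes and listings are not counts of subjects who changed category.

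Two further inferences go too far. One is that Final Evaluation falls later in the active arm. The exit rule makes that plausible if the drug works, but the visible text gives no duration of effect from which to show it or size it. The other is that Week 4 is when a laboratory effect is most likely; nothing in the visible text says so.

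Finally, the SAP introduction refers to table shells that are not in the supplied text. They may already include Week 4. If so, the wording of 4.8.4.1 needs to be brought into line with them.

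**Conclusion.** The point holds as a limited gap in safety reporting. As written, SAP 4.8.4.1 provides no by-arm count of hematology, chemistry and PT category changes at Week 4, and a shift that resolves before Final Evaluation enters no shift table. It would still appear in the listing, would contribute to the Week 4 summaries if the test is continuous, and would reach the adverse-event tables if reported as an event.

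The gap is one of the two planned post-treatment visits in one type of output. It affects no endpoint definition, hypothesis test or sample collection. The conclusion rests on the explicit SAP sentence and on reading the shift tables as by treatment group. That sentence does not say so itself, but the surrounding text implies it. Protocol 7.6.2 has the same restriction, but Protocol 7.1 leaves the description of all analyses to the SAP, so the SAP is where the change belongs.

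**What to change.** In SAP 4.8.4.1, specify shift tables by treatment group for three comparisons: Screening to Week 4, Screening to worst post-treatment value, and Screening to Final Evaluation as now planned. For the worst-value table, say that the lowest and highest post-treatment categories are tabulated separately where a test has both limits, and whether unscheduled repeats count, since Protocol 4.5.1 allows repeat tests. Check the table shells against the new wording. A protocol amendment is not needed for this.

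The cost is a short change to the SAP text and a few extra tables from the same program. No new samples or data collection are required.

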4.8.4.2. Pregnancy Tests

Urine pregnancy tests will be presented in data listings for all treated patients in the category of woman of child-bearing potential.

4.8.6. Vital Signs, Physical Examination, and ECG

[figure not shown]
Vital signs and ECG parameters will be summarized by treatment group with descriptive statistics for each treatment group by visit. Vital signs and ECG parameters will summarize the actual value as well as the change from screening for each visit using the number of non-missing observations, mean, median, minimum, maximum and standard deviation. The overall ECG assessment will be summarized for each treatment group using number and percentage of patients with a normal, abnormal and clinically significant, or abnormal and not clinically significant result.

[figure not shown]
Abnormal findings from the physical examination

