4.2.2 TREATMENT VISIT (DAY 0)

The Treatment Visit must be performed within 14 days of the Screening Visit. The following procedures must be performed and recorded:

Prior to Investigational Product Administration

1. Review eligibility criteria and confirm that all screening visit procedures have been completed, results reviewed, and recorded
2. Update medical/surgical history
3. Conduct patient education: Discuss the potential effect of DaxibotulinumtoxinA for Injection treatment, explain the PFWS measurement and the categories of the severity assessment scales, and instruct the subjects to consider depth of lines for severity of their glabellar lines. Use the provided Patient Education Brochure

4. Inject a dose of [REDACTED]
[REDACTED]
[REDACTED]
■ [REDACTED]

After Investigational Product Administration

1. [REDACTED] obtain vital signs (body temperature, respiratory rate, sitting radial pulse, and sitting systolic and diastolic blood pressures)
■ [REDACTED]
■ [REDACTED]
■ [REDACTED]
[REDACTED]
[REDACTED]
[REDACTED]
■ [REDACTED]
■ [REDACTED]
[REDACTED]
[REDACTED]
■ [REDACTED]
■ [REDACTED]
[REDACTED]
[REDACTED]
[REDACTED]
[REDACTED]
■ [REDACTED]
[REDACTED]
[REDACTED]

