7.6.3 VITAL SIGNS AND PHYSICAL EXAMINATION

Vital signs and abnormal findings from the physical examination will be summarized with descriptive statistics for each treatment group by visit.

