3.3.5. Vital Signs

Vital signs (i.e., body temperature, respiration rate, sitting radial pulse rate, and sitting systolic and diastolic blood pressures) will be obtained at the Screening and Treatment Visit (pre- and post-treatment), Week 2, Final Evaluation or Early Discontinuation Visits and at any visit where signs or symptoms of botulinum toxicity are reported.

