3.3.6. Physical Examination

A physical examination, in addition to vital signs,

, general appearance, skin, neck (including thyroid), eyes, ears, nose, throat, heart, lungs,

abdomen, lymph nodes, and extremities will be conducted at Screening, Week 2 and Final Evaluation or Early Discontinuation Visits. Significant physical examination findings that are present prior to investigational product administration are to be included on the Medical History page.

Significant physical examination findings which meet the definition of an adverse event will be recorded on the adverse event page post-treatment.

3.3.7. 12-Lead ECG

At Screening and Week 4, a single standard supine 12-Lead ECG will be obtained.

[figure not shown]

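### Vital-sign change is referred to Screening at every visit, so the same-day pre- to post-injection change is not planned in the readable text (minor, free improvement)

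*SAP*

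**What the plan says.** SAP 4.8.6 gives the summary rule: "Vital signs and ECG parameters will summarize the actual value as well as the change from screening for each visit". One sentence covers both vital signs and ECG and names one reference for all visits.

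SAP 3.3.5 gives the measurement times. Vital signs "will be obtained at the Screening and Treatment Visit (pre- and post-treatment), Week 2, Final Evaluation or Early Discontinuation Visits", and also at any visit where signs of toxin effect are reported. Protocol 4.5.3 has the same schedule. Protocol 4.2.2 confirms the reading after administration: "obtain vital signs (body temperature, respiratory rate, sitting radial pulse, and sitting systolic and diastolic blood pressures".

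The interval comes from Protocol 4.2.1: "The Screening Visit must take place within 14 days prior to investigational product administration at Day 0".

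For ECG the schedule is different (SAP 3.3.7): "At Screening and Week 4, a single standard supine 12-Lead ECG will be obtained".

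Protocol 7.6.3 names neither a change score nor a reference point: "Vital signs and abnormal findings from the physical examination will be summarized with descriptive statistics for each treatment group by visit". The SAP sentence therefore governs. No readable text defines another vital-sign baseline or plans a Day 0 pre-to-post change; what can be read of SAP 4.9.5 deals only with day numbering.

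**The concern.** Two readings a short time apart, on either side of an injection, are the natural way to see an immediate effect on pulse or blood pressure. Each patient is their own control within one visit. The SAP compares the second of these readings with one taken at another visit, up to two weeks earlier. The resulting change mixes any acute response with whatever happened between Screening and Day 0, including ordinary visit-to-visit variation and any first-visit effect.

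What is at stake is the informativeness of one descriptive safety table. The spread and extremes of the paired Day 0 change, which would show a patient with a marked acute shift, are not among the planned summaries that can be read.

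**Working it through.** **1. No figure to reproduce.** The documents state no SD, correlation, power or threshold for vital signs. What can be checked is the structure of the rule and, under stated assumptions, its effect on precision.

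**2. What change from Screening contains.** For one patient,

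(post − Screening) = (post − pre) + (pre − Screening).

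The first term is the acute change. The second lies wholly before injection. The SAP summarises the sum.

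**3. Effect on the mean.** Screening and the pre-injection reading both precede treatment, so randomisation gives the second term the same expected value in both arms. It cancels from the active-minus-placebo difference. The choice of reference can shift the mean change within an arm, but not the expected contrast.

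**4. Effect on the spread.** Assume the same SD, s, at each reading, and let r be the correlation between the reference and the post-injection value. Then

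SD(change) = s × √(2(1 − r)).

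Assumed ranges, for illustration only: same-day r from 0.7 to 0.9; Screening r from 0.5 to 0.7. The table gives the SD of the Screening-based change divided by the SD of the same-day change, √((1 − r_Screening)/(1 − r_same-day)).

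| Same-day r | SD from pre-injection | Screening r = 0.5 (SD 1.000s) | Screening r = 0.6 (SD 0.894s) | Screening r = 0.7 (SD 0.775s) |
|---|---|---|---|---|
| 0.7 | 0.775s | 1.29 | 1.15 | 1.00 |
| 0.8 | 0.632s | 1.58 | 1.41 | 1.22 |
| 0.9 | 0.447s | 2.24 | 2.00 | 1.73 |

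Middle case, 0.8 against 0.6: √(2 × 0.2) = 0.632 and √(2 × 0.4) = 0.894. The same-day SD is 1 − 0.632/0.894 = 29% smaller, and the Screening-based variance is 0.8/0.4 = 2 times as large.

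With the planned arms of 200 and 100 (Protocol 3.1.3, Table 1), a 95% interval for the arm difference in mean change would have half-width 1.96 × SD × √(1/200 + 1/100) = 1.96 × 0.1225 × SD. That is 0.152s with the same-day reference and 0.215s with Screening. The readable plan calls for no such interval on vital signs; this only shows scale.

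If the two correlations are equal, the ratio is 1.00 and there is no loss of precision. The acute change itself would still not be reported.

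**5. What the planned table lets a reader recover.** Actual values are also summarised by visit. If pre- and post-injection readings have separate rows, which SAP 4.8.6 does not state, then with complete data the difference of the two means equals the mean paired change. The SD, median, minimum and maximum of the paired change cannot be recovered from the separate summaries.

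**The case against.** The strongest opposing points are these.

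- **Unseen material.** SAP section 1 says table shells follow the text, and they are not in the text available. Material around 4.8.6 and in 4.9 is also missing. Shells could show Day 0 pre and post as separate rows, or a paired change. This stands as a limit: the point applies to the visible sentence. That sentence does name Screening for every visit, so a different convention elsewhere would need reconciling with it.
- **Little depends on precision here.** SAP 4.8 makes the safety analysis descriptive, and no test or decision rule for vital signs can be read. Protocol 6.1 requires any clinically significant post-treatment change in vital signs to be reported as an adverse event, whatever baseline the summary uses. This stands, and keeps the severity low.
- **One common reference is consistent.** SAP 4.8.4.1 also measures laboratory change from Screening, and a reading just before injection may be affected by anticipation. The first part does not carry over, because the laboratory schedule in SAP 3.3.3 lists Screening as its only pre-treatment sample. The second is a fair reason to keep the actual Screening values in the table.
- **The gain is shown only for the Day 0 post-injection reading.** At Week 2 and Final Evaluation either reference is weeks away. This stands.

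A reader might also infer that the older reference dilutes a true acute effect, or biases the comparison with placebo. Step 3 of the working shows otherwise: it adds variance, while the expected arm difference is unchanged. Nor do the documents support a claim that individual acute events would go unrecorded, given the adverse-event rule.

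**Conclusion.** The point holds as a minor, no-cost improvement to a descriptive safety table. On the readable text, SAP 4.8.6 refers vital-sign change to a reading up to 14 days before injection although a same-day pre-injection reading is scheduled, and it does not plan the within-patient change across the injection.

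The loss is in precision and in the missing paired summaries. Its size cannot be fixed from the documents. Under equal SDs and the assumed correlations, the Screening-based SD is 1.00 to 2.24 times the same-day SD. The 29% reduction in the middle case is an illustration, not an estimate for this trial. The lower end, no loss, applies when a reading up to 14 days old correlates with the post-injection value as well as a same-visit one does.

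No efficacy conclusion, error rate or randomised contrast is affected. The point does not extend to ECG.

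**What to change.** In SAP 4.8.6, separate vital signs from ECG:

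- Define the vital-sign baseline as the last non-missing value before injection: normally the Day 0 pre-treatment reading, with Screening used if that is missing.
- Report the Day 0 pre-to-post change by treatment group with number, mean, SD, median, minimum and maximum.
- Use the same baseline at Week 2 and Final Evaluation for consistency only; no precision gain is shown there.
- Keep actual values for Screening and for each Day 0 reading as separate rows.
- Keep Screening as the reference for ECG.

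If the table shells already contain the Day 0 paired change, it is enough to confirm this and bring the sentence in 4.8.6 into line. The cost is one SAP sentence and one derived variable, with no new data and no change to trial procedures.
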